# 15.3. Planned final analyses

The primary analysis for the trial will occur once all participants have completed the 6 month assessment and corresponding outcome data has been entered onto the trial database and validated as being ready for analysis.

## 16. HEALTH ECONOMICS

The aim of the health economic analysis is to assess the cost-effectiveness of the F4S App in patients undergoing lung surgery. Following an agreed Health Economics Analysis Plan and in line with the National Institute for Health and Care Excellence (NICE) reference case [59], the analysis will be carried out from the perspective of the NHS and Personal Social Services. Subsequently, additional analyses will be carried out from a societal perspective.

#### **16.1.** Within-trial economic evaluation

A within-trial based economic evaluation will explore the cost-effectiveness of the 2 alternative interventions being compared i) usual care ii) F4S App.

#### Resource use and costs

Data collection will be carried out prospectively and will include resource use and costs due to delivering the intervention, including staff time, counselling, training costs and cost of medication; Use of health care and community services, including hospital admissions, length of hospitalisation, outpatient appointments, appointments with general practitioners, nurses and allied health care professionals; Patient out-of-pocket expenditure (e.g. travel costs), and time lost from work. Resource use will be obtained from patient completed questionnaires and through the App.

To obtain a total per-patient cost, resource use will be combined with the unit cost values obtained from national sources and tariffs, including the Unit Cost of Health and Social Care report, the British National Formulary and the NHS Reference Cost Schedules [60,61].

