### 1. BACKGROUND AND RATIONALE

# 1.1. Background

Surgery remains the best option for the cure of patients with lung cancer. Seven thousand such operations are performed in the United Kingdom (UK) each year, but post-operative complications occur in up to 45% of patients leading to readmission to hospital (13%), and up to a 5-fold increase in treatment costs. [1-4] Lung complications account for half of the post-operative complications. In these patients, 30 day mortality increases from 0.7 to 9%, Intensive Care Unit (ICU) admission rate from 1.9 to 28%, and hospital length of stay from 6 to 13 days. [5]

The burden to patients and to the National Health Service (NHS) continues to rise despite changes in surgery practice. Since 2015, there has been a sustained policy aiming to increase the numbers of patients receiving curative lung cancer surgery in order to improve the UK's poor ranking; 26th out of 29 European countries in lung cancer outcomes. [6] Thus, surgery is being offered to older and less fit patients, and the number of operations performed annually across the UK has increased by 12% over the last 3 years. [1,7]

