#### 7.4. Intervention Modification or Cessation

The F4S App will not be available to participants who are randomised to the usual care arm of the trial, so crossover will not be possible from usual care. It is possible that participants randomised to the F4S arm will cease to engage with the App completely. This will not however be considered a crossover, since this is part of the pragmatic nature of the trial.

As mentioned in section 7.3 the App is designed to adapt to the participant as they use it, or cease to use it. The variability in engagement with the App forms part of the trial and will be captured by the App.

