# 7.6. Intervention Access Supply and Storage

Participants will be asked to download the F4S App to their personal device. A link to register for the App will be provided to all participants randomised to the F4S arm. For those who do not have a mobile device, tablets will be provided before surgery and for approx. 6 weeks after. The tablet devices will be distributed to the recruiting sites from the Trial Office, where they should be safely secured until provided to a participant.

When provided to a participant the equipment log should be completed to record tablet use. At the end of each participant's participation in the trial the tablet will be returned to the recruiting site. The site will maintain a log of usage of the Tablet, set used throughout the study recording the lot number used against each participant (on an equipment log). The hardware does not require any special storage conditions but should be handled with due care and in accordance with any instructions. Equipment failures will be replaced provided there is no evidence of inappropriate use or deliberate negligence, under which circumstances the Sponsor reserves the right not to re-supply the participant.

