## 30 days post-Surgery

- Assessment of complications post hospital discharge (Comprehensive Complication Index (CCI))
- Nutritional assessment including weight (PG-SGA SF)
- Physical tests Muscle strength hand grip, ISWT and sit to stand test
- Participant completed questionnaires to include EORTC-QLC-C30 & LC29, EQ-5D-5L,
   HADS
- Post-operative questions assessing usual care
- Post-operative Nutritional input assessment (drinks and dietitian)
- Health resource usage questionnaire

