# 10. ADVERSE EVENT REPORTING

No related harms have been reported in the literature regarding App use to facilitate self-management of diet and exercise. Therefore, there is no reason to anticipate any safety concerns arising as a result of this intervention within F4S-2. Events that would be considered as adverse events (AEs) are being collected as part of the outcome measures data collection up to 30 days post-surgery this will include the following:

- Post-operative complications as per Claviden-Dindo classifications see appendix I
- In-hospital mortality
- 30 day mortality

During follow-up, the systematic collection of self-reported data as part of the clinical outcomes will be conducted, this will take place alongside routine medical note review (at mandated time points: day of discharge and 30 days follow up). This will include participant reported summaries of health care visits including any admissions to accident and emergency. The team will also capture whether there have been any deaths and cause of death. The events listed above (with reference to Appendix I) will be reviewed by the Data Monitoring Committee (DMC) at regular intervals as part of the main data set.

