**Table 3: Source Data** 

Data	Source	
Participant Reported Outcomes (including Health Economics data).	The original completed participant reported outcome booklet is the source documentation. These will be either be stored with the participant's trial record:  • at site, where the questionnaires have been administered by site in clinic  • at Trial Office, where the questionnaires have been posted by and returned to the Trial Office	
Clinical event data	The original clinical annotation is the source document.  This may be found on clinical correspondence, or electronic or paper participant records. Clinical data reported by the participant, either in or out of clinic (e.g., phone calls), must be documented in the source documents.	
Data uploaded to the F4S App	User usage and engagement data will be transferred to BCTU servers in the form of JSON files and will be the source documentation.	
Recruitment	The original record of the randomisation is the source. It is held on BCTU servers as part of the randomisation and data entry system.	
Withdrawal	Where a participant expresses a wish to change their level of participation, the conversation must be recorded in the medical records, and this will constitute the source data.	

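### Section 16.1 takes inpatient resource use from patient questionnaires and the App, which cannot supply it for participants who die before day 30 or do not respond

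*Protocol*

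**What the plan says.** Under Resource use and costs, section 16.1 lists the items to be costed, among them "Use of health care and community services, including hospital admissions, length of hospitalisation, outpatient appointments". It then fixes where the data come from: "Resource use will be obtained from patient completed questionnaires and through the App". Table 3 (section 12.1) has a row headed "Participant Reported Outcomes (including Health Economics data", for which the original completed booklet is the source document.

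The two named sources are limited:

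- **App.** Section 7.4 states "The F4S App will not be available to participants who are randomised to the usual care arm of the trial".
- **Questionnaire.** The section 9 visit lists and Table 2 place the "Health resource usage questionnaire" at 30 days and 6 months after surgery, and at no other time.

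Elsewhere the protocol opens the hospital record. Section 10 provides for "routine medical note review (at mandated time points: day of discharge and 30 days follow up" and for capture of deaths and their cause. DAH30 (section 8.2.2) cannot be derived without days in hospital and death to day 30.

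The Analysis paragraph of section 16.1 says missing data will be handled by suitable techniques, with multiple imputation as an example. Section 16 refers to a Health Economics Analysis Plan, which is not at hand.

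**The concern.** Cost-effectiveness is part of the primary objective (section 2.2). The economic rationale in section 1.2 is that prehabilitation saves money through shorter stay and fewer complications, ICU admissions and readmissions. The Analysis paragraph of section 16.1 itself notes that cost is skewed by a few very expensive patients.

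A source that depends on the patient answering is weakest for those patients. Someone who dies before day 30 cannot complete the form, and someone with a difficult recovery is less likely to. If inpatient cost is under-recorded where complications occur, the arm with more complications loses more of its cost. The difference in cost, and so the ICER, is distorted.

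**Working it through.** The protocol gives no figure for completeness of economic data, so there is none to reproduce. The calculations below gauge size only.

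**Inputs.**
- Section 1.1: complications in up to 45% of patients, half of them lung complications, so the proportion with a lung complication is at most p = 0.45 × 0.5 = 0.225.
- Section 1.1: without and with a lung complication, 30-day mortality is 0.7% and 9%, and stay is 6 and 13 days.
- Section 15.1: 902 participants and 20% attrition.
- Assumed: a lower value of p = 0.10, because 45% is an upper limit; and the non-response rates in step 3.

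**1. Coverage of the named sources.**

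| Participant | App | 30-day form | 6-month form |
|---|---|---|---|
| Usual care, dies before day 30 | not available | not completed | not completed |
| F4S, dies before day 30 | cannot report the terminal stay | not completed | not completed |
| Usual care, non-responder | not available | missing | missing |
| Dies between day 30 and 6 months | F4S only | may be present | not completed |

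In usual care the first and third rows have no source at all.

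**2. Deaths alone.** 30-day mortality = 0.09p + 0.007(1 − p).
- p = 0.225: 0.02025 + 0.00543 = 2.57%, or 23 of 902.
- p = 0.10: 0.0090 + 0.0063 = 1.53%, or 14 of 902.

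True mean stay = 6 + 7p. Mean stay among survivors = [13 × 0.91p + 6 × 0.993(1 − p)] / (1 − mortality), if those who die have the mean stay of their group.
- p = 0.225: 7.575 against 7.471 days, 0.10 days too low (1.4%).
- p = 0.10: 6.700 against 6.647 days, 0.05 days too low (0.8%).

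**3. Selective non-response.** Let 20% of forms be missing overall, and a fraction m be missing among patients with lung complications. Their share among responders is p(1 − m)/0.80, and mean stay among responders is 6 + 7 × share.

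| p | m | True mean | Responder mean | Shortfall |
|---|---|---|---|---|
| 0.10 | 0.40 | 6.70 | 6.52 | 0.18 (2.6%) |
| 0.10 | 0.60 | 6.70 | 6.35 | 0.35 (5.2%) |
| 0.225 | 0.40 | 7.58 | 7.18 | 0.39 (5.2%) |
| 0.225 | 0.60 | 7.58 | 6.79 | 0.79 (10.4%) |

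**4. Effect on a difference.** Suppose lung complications are truly 22.5% in usual care and 15% with F4S. The true difference in stay is 7 × 0.075 = 0.53 days.
- With 20% missing in each arm, responders show 7 × 0.075 × 0.60/0.80 = 0.39 days at m = 0.40, or 7 × 0.075 × 0.40/0.80 = 0.26 days at m = 0.60. The loss is 25% to 50%.
- If instead non-response by complication status is the same in both arms, with the rate in uncomplicated patients set by the usual-care arm (14.2% or 8.4%), responders show 0.41 or 0.29 days. The loss is about 21% to 45%.

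Stay leaves out the extra daily cost of critical care. Responder means also show the result before any imputation; a good imputation model could recover part of the loss.

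**The case against.** **The sentence may not be exhaustive.** It does not say that no other source will be used, and its own paragraph lists staff time and training costs, which no patient could report. It may be loosely drafted. But for hospital admissions and length of stay it is the only source given, and Table 3 repeats the choice.

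**The Health Economics Analysis Plan may settle this.** It can choose a missing-data method. It cannot recover critical-care days or readmission dates that nobody entered.

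**Much of the information is held already.** Clavien-Dindo grades are assessed at discharge and day 30, Table 3 takes clinical events from the clinical record, and DAH30 needs days in hospital. This stands. It makes the gap narrow: a source for costing has to be named, and a few items recorded.

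**Non-response may be modest.** Section 12.3 has the 30-day booklet completed in clinic with staff support, and Table 2 allows a window of 7 days either side. This also stands, and is why the rates in step 3 are assumptions and not predictions.

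Three stronger readings are tempting and not supported:
- A reader might infer that the costs of those who die will be imputed from survivors. Section 16.1 names multiple imputation only as an example and says nothing about deaths or donors.
- A reader might price every death at the top of "up to a 5-fold increase in treatment costs" and find a large loss from deaths alone. Section 1.1 gives that as an upper limit for complications generally, not as the cost of a death.
- A reader might extend the point to delivery items such as tablets. Section 16.1 already commits to collecting delivery costs and section 7.6 keeps an equipment log; what remains there is unstated detail, not a wrong rule.

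**Conclusion.** The point holds as a flaw in a stated data source. As written, section 16.1 and Table 3 provide no route to inpatient costs for participants who die before day 30 or do not respond. Those costs would be missing, or would depend on whichever missing-data method is later chosen.

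Deaths by themselves have a small effect: at most about 2.6% of participants and about 1% of mean stay, taking the upper complication rate and average stays for those who die. Selective non-response among patients with complications is the larger risk. Its size cannot be read from the protocol; the losses in step 4 show only what assumed rates of 40% to 60% would do. The direction, a true saving made to look smaller, rests on non-response among complicated patients being similar in the two arms. No effect on the ICER has been calculated. This is a worthwhile, inexpensive improvement and not a threat to the trial.

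**What to change.** Replace the source sentence in section 16.1 with wording such as:

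> Index stay, critical-care days and readmissions to day 30 will be taken from hospital records at the discharge and day-30 note reviews, in both arms and including participants who die. Questionnaires will supply primary care, community care, out-of-pocket cost and time off work.

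Amend the health economics row of Table 3 to match.

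The cost is a few extra eCRF fields and a little data-entry time at sites, from notes already being read. The change reaches only to day 30, because the protocol mandates no note review after that; hospital use from day 30 to 6 months would still rest on the 6-month questionnaire. It should be made while data are still being collected, since items not recorded then may not be recoverable at analysis.

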### **Quality of life**

Quality of life will be derived from patients' responses to the EuroQol EQ-5D-5L instrument over the follow up period [62]. Each patient's health status descriptions obtained from the EQ-5D-5L will be translated into a single, preference-based index following NICE guidelines. QALYs will be calculated as the area under the curve approach.

#### **Analysis**

The trial-based analysis will be conducted on an 'intention to treat' basis. Missing data will be accounted for by using appropriate techniques, such as multiple imputation, depending on the extent and type of missing items. As the distribution of cost is usually skewed by the existence of patients with particularly high costs, the calculated mean per-patient cost will be given alongside confidence intervals obtained through non-parametric bootstrap methods. Incremental analysis will be undertaken to calculate the difference in costs and relevant outcomes of the interventions compared. Results will be presented in the form of incremental cost-effectiveness ratios (ICER), reflecting the additional cost per QALY gained. Where appropriate, the joint distribution of cost and outcomes derived from bootstrap simulations will be depicted on a cost-effectiveness plane and will be plotted as cost-effectiveness acceptability curves (CEACs) which will indicate the probability of F4S-2 intervention being cost-effective across a range of possible values of willingness to pay. Sensitivity analyses will be undertaken to explore the impact of alternative values and assumptions on the obtained results.

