#### **Day of Surgery**

- Nutritional assessment including weight (PG-SGA SF)
- Physical tests Muscle strength hand grip and sit to stand test
- Participant completed questionnaires to include EORTC-QLC-C30 & LC29, EQ-5D-5L,
   HADS
- Pre-operative questions assessing usual care
- Pre-operative Nutritional input assessment (drinks and dietitian)

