## 6 months post-Surgery

- Participant completed questionnaires to include EORTC-QLC-C30 & LC29, EQ-5D-5L,
   HADS
- Health resource usage questionnaire
- Assessment of disease recurrence/progression

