**Table 2: Schedule of Assessments** 

Trial Procedures and		Day of Surgery	Day of Discharge	14 days Post op	30 days Post op	3 months Post op	6 months Post op
Assessments	Doseline	(- 1	(+/- 2	(+/- 3	(+/- 7	(+/- 2	(+/- 4
	Baseline	days)	days)	days)	days)	weeks)	weeks)
Medical history	Х						
Informed consent	X						
Randomisation	Х						
Patient and/or Carer	X						
Instructions for use of							
Арр							
Nutritional assessment	Х	Х			Х		
(incl. height and							
weight) - PG-SGA SF							
Nutritional input		Х			Х		
assessment (drinks and							
dietitian)							
Physical tests (incl.	Х	Χ*	Х		Х		
hand grip, ISWT, sit to		(ISWT not collected)	(ISWT not collected)				
stand test)			conected)				
Participant completed	Х	Χ*		Х	Х	X	Х
questionnaires (incl.							
EORTC-QLQ-C30 &							
LC29, HADS, EQ-5D-5L)					.,		
Health Resource Usage					Х		Х
questionnaire							
Questions assessing		Χ*			Х		
Usual Care							
Assessment of clinical			X		Х		
complications (CCI)	.,						
Technology Access	Х						
Questions Assessment of disease							V
							Х
recurrence/progression	(IN VDDI		OVE INTERVE	NTION ADI	M ONLY)		
Participant completed	ווע אטוו)	X	OAT HAITKAE	-14 HON ARI	X	Х	
Motivational Processes		^			^	^	
Participant completed		X			X	X	
Shortened Scale of		^			^		
Behavioural Change							

\* In instances where the participants surgery is cancelled and rearranged, the physical tests will need to be repeated if it is **more than 7 days** from the original surgery date. If the participant has already completed the Day of Surgery Participant Booklets they will be required to completed again.

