# 15.2. Analysis of outcomes

A separate Statistical Analysis Plan (SAP) will be produced and will provide a more comprehensive description of the planned statistical analyses. A brief outline of these analyses is given below.

The primary comparison groups will be composed of those participants randomised to the F4S App and Usual Care versus those randomised to Usual Care alone. All analyses will be based on the modified intention to treat principle, i.e., participants will be analysed in the intervention group to which they were randomised irrespective of adherence to randomised group or other protocol deviations, will only include those who received surgery.

For all outcomes, appropriate summary statistics and differences between groups, e.g. mean differences, will be presented. Where possible intervention effects will be adjusted for the minimisation variables listed in Section 6.2.3, and baseline values (where available). Given the structure of the data, nesting of patients by centre, centre will be included in the model in the primary analysis.

For the dual primary outcomes, differences between groups will be presented alongside 97.5% confidence intervals and p-values from two-sided tests also provided. To maintain an overall 5% Type I error rate, each comparison will be tested at a significance level of 2.5% to account for the increase in the risk of type I error associated with making two key comparisons. Thus, statistical significance will be set to p<0.025 (two sided). All secondary outcomes will be presented with 99% confidence intervals and no p-values.

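### Section 16.1 plans an intention-to-treat economic analysis, but section 15.2 limits all analyses to operated participants, and every post-baseline EQ-5D-5L point and both resource-use questionnaires are timed from surgery

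*Protocol*

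**What the plan says.** The protocol makes two statements about the analysis population. Section 15.2 says "All analyses will be based on the modified intention to treat principle", keeps participants in their allocated arm, and adds that the analyses "will only include those who received surgery". It does not exempt section 16. Section 16.1, under Analysis, says "The trial-based analysis will be conducted on an 'intention to treat' basis", without the qualifier and without mentioning surgery.

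QALYs are the area under the EQ-5D-5L curve (16.1, Quality of life). Resource use comes from participant questionnaires and the App (16.1, Resource use and costs). Section 9 and Table 2 fix when these are collected:

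- EQ-5D-5L: at baseline; on the day of surgery, where the entry reads "Participant completed questionnaires to include EORTC-QLC-C30 & LC29, EQ-5D-5L"; and at 14 days, 30 days, 3 months and 6 months after surgery.
- Resource use: "Health resource usage questionnaire" appears at 30 days and at 6 months after surgery, and nowhere else.

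The only rule for disrupted surgery is the Table 2 footnote: "In instances where the participants surgery is cancelled and rearranged, the physical tests will need to be repeated" once a stated delay is exceeded, and "If the participant has already completed the Day of Surgery Participant Booklets they will be required to completed again". It covers postponement. Section 9.1 covers participants who choose to reduce their participation. Neither covers an operation that never takes place.

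**The concern.** The intervention is delivered mainly before surgery, so being operated on is an event that happens after randomisation. Non-operation is foreseeable: section 15.2 restricts its population because of it, entry requires only a suspected diagnosis (4.1), and baseline is at least two weeks before the operation (section 9).

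Under intention to treat in its usual sense, these participants belong in the cost-effectiveness result, but the schedule collects almost nothing from them after baseline. An analysis plan can settle the population or the imputation model later. It cannot supply questionnaires that never fell due. Cost-effectiveness is part of the primary objective (2.2), so this is not a side analysis.

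**Working it through.** **Counting what falls due.** The protocol gives no figure on this point to reproduce, so the first step is a count from section 9 and Table 2.

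- EQ-5D-5L: 6 points, 1 at baseline and 5 timed from surgery. A never-operated participant has 1 of 6. If surgery is cancelled after the day-of-surgery booklet is completed, 2 of 6.
- Resource-use questionnaires: 2, both timed from surgery. A never-operated participant has 0 of 2.
- Other sources: the App is closed to the usual care arm (7.4), so it could fill gaps in one arm only. The mandated note review in section 10 is set at discharge and at 30 days, so it too follows the operation.

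**How many people.** The protocol states no never-operated rate. Its only loss figure is 20% attrition (15.1), not split by cause: 902 × 0.20 = 180.4. Assumed rates give:

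- 2%: 902 × 0.02 = 18.0
- 5%: 902 × 0.05 = 45.1
- 10%: 902 × 0.10 = 90.2

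**What omission or imputation does.** Let p1 and p0 be the proportions operated on in the F4S and usual care arms, a1 and a0 the mean cost (or QALY) if operated on, and b1 and b0 the mean if not.

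- All-randomised difference = p1·a1 + (1−p1)·b1 − p0·a0 − (1−p0)·b0
- Operated-only difference = a1 − a0. Giving unoperated participants the operated mean of their own arm yields the same value.

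Two special cases show what the gap between them depends on:

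(a) Arms alike within each stratum (a1 = a0 = a, b1 = b0 = b). Gap = (p1−p0)·(a−b). Each percentage point of arm difference in the proportion operated on gives 0.01 × £1,000 = £10 per £1,000 of cost difference between operated and unoperated participants, and 0.01 × 0.1 = 0.001 QALY per 0.1 QALY of difference.

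(b) Equal proportions unoperated (p1 = p0 = 1−q). Gap = q·[(b1−b0) − (a1−a0)]. For each £1,000 by which the arm difference in the unoperated departs from that in the operated, the shift is 0.02 × £1,000 = £20 at q = 2% and 0.10 × £1,000 = £100 at q = 10%.

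If p1 = p0 and b1−b0 = a1−a0, the gap is zero. The £1,000 and 0.1 QALY are units for scaling, not estimates.

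**The case against.** The strongest reply is that the economic question concerns operated patients. Section 16 opens by framing its aim around people having lung surgery, and section 15.2 speaks of all analyses. On that reading surgery-timed collection is what the question needs, and the fault is one loose phrase in 16.1. The reading is possible, but it does not remove the problem. If 15.2 governs section 16, the intention-to-treat statement in 16.1 is contradicted; if it does not, the data for that analysis are not scheduled.

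A second reply is that section 16 defers to a Health Economics Analysis Plan and 16.1 allows multiple imputation and sensitivity analyses. This stands for the population, the time origin and the choice of sensitivity analysis. It does not stand for collection, which is a matter for the protocol's schedule. With almost no post-baseline values from unoperated participants, the trial data could not test an imputation that borrows from operated ones.

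Three stronger readings are tempting, and the protocol does not support them:

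- That it has no rule at all for never-operated participants. Section 15.2 does cover them, by exclusion; what is missing is a follow-up rule.
- That nothing could be recovered. Consent includes direct access to medical records (5.2) and the NHS number is held (section 20), so some hospital use could be retrieved later.
- That the economic result will be biased. Nothing in the protocol shows that the proportion operated on, or the arm difference among the unoperated, will differ in the way that matters. Prehabilitation makes a difference plausible, no more.

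**Conclusion.** The point holds as an inconsistency between 15.2 and 16.1 together with a gap in collection. As written, an intention-to-treat economic analysis would have to impute never-operated participants from operated ones or leave them out. What would be permanently lost is their EQ-5D-5L, out-of-pocket costs and time off work.

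The size cannot be derived from the protocol. The range of 18-90 participants rests on an assumed 2-10% never-operated rate, and the effect on the incremental result may be zero under the conditions shown above. The sample size and the two clinical primary outcomes are not affected. This is a cheap improvement worth making because collection cannot be repaired at the analysis stage.

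**What to change.** Add a Table 2 footnote: randomised participants who are not operated on are posted the existing EQ-5D-5L and resource-use booklets at 30 days, 3 months and 6 months from the originally planned surgery date, and the reason for no surgery is recorded. If no date was set, time them from randomisation plus one interval, fixed in advance and identical in both arms. The anchor has to be stated because the protocol gives a minimum of two weeks to surgery but no expected or maximum interval.

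State in 15.2 that the surgery-only restriction does not apply to section 16. State in 16.1 that costs and QALYs are counted from randomisation for everyone and that the operated-only analysis is a sensitivity analysis.

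The cost is an amendment with its approvals and a small mailing (an assumed 18-90 people over the trial). The Trial Office already posts the 3- and 6-month booklets (12.3); the 30-day booklet, normally completed in clinic, would be posted for this group. Return rates may be lower among people who have left the surgical pathway, and the area-under-the-curve calculation would have two follow-up time scales to align.
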